5.9.3 Serious Adverse Events

All serious adverse events (SAE's) occurring during the 90 days of study participation will be recorded. Adverse events and serious adverse events are critical endpoints and will be assessed as they occur and at the scheduled clinic visits. A serious adverse event is one that is fatal or life-threatening, is permanently or substantially disabling, requires or prolongs hospitalization, or any event that the treating clinician judges to be a significant hazard, contraindication, side effect, or precaution. For each recorded adverse event, the patient's attending physician will be asked to classify the causal relationship of the event to the study treatment as definitely related, probably related, possibly related, unlikely related, or not related. Especially detailed form and narrative reports of the following specific adverse events will be obtained:

- Neurologic Deterioration: Increase of 4 or more points in the NIHSS
- Symptomatic Hemorrhagic Event: an ECASS defined ICH visualized on follow-up imaging study and associated with a 4 or more point worsening on the NIHSS score*
- Angiographic or thrombectomy procedural complications: Groin hematoma requiring transfusion or surgery, vessel dissection, vessel perforation, presence of emboli in a previously uninvolved territory, or other unanticipated procedure-related event, device fracture
- Malignant cerebral edema: Edema associated with neurologic impairment or requiring medical or surgical intervention
- Subarachnoid Hemorrhage (SAH): Both symptomatic and asymptomatic SAH visualized on follow-up imaging study.

*Asymptomatic hemorrhage events are not considered serious adverse events

An unblinded Safety Monitor will review all serious adverse events individually on a continuous basis as they occur and aggregate unblinded data on adverse events quarterly. This individual will report independently to the appointed DSMB at regularly scheduled DSMB meetings. This individual also has the authority to alert the DSMB at any time if a potential safety issue arises. If at any point, these reviews raise any safety concerns, the DSMB will be empowered to suggest that the trial be placed on hold and request additional analyses of the trial dataset.

6. Study Primary Endpoints

The primary objective is to show that AIS patients, ineligible for or refractory to treatment with IV-tPA, Patients seen within 6 hours of symptom onset will be immediately considered for endovascular therapy according to the site's standard of care. Likewise, patients presenting beyond 12 hours will be treated according to the site's standard of care. with appropriate image selection, treated within 6-12 hours with mechanical thrombectomy have superior rates of good functional outcomes as compared to those treated with best MT with respect to endpoint defined as:

- 90-day global disability assessed via the modified Rankin score (mRS), analyzed using raw mRS scores. Statistical details can be found in section 7.2.

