7.5 Safety Analysis

7.5.1 Safety Outcomes

Several specific adverse events will be monitored throughout the study. However the primary safety outcomes to be assessed at completion of the trial are:

- Symptomatic intracranial hemorrhage at 24 hours post-randomization
- Asymptomatic intracranial hemorrhage at 24 hours post-randomization
- Intracranial hemorrhage within 90 days of hospital discharge
- Clinically significant complications (pneumonia, sepsis, UTI, etc.) at time of discharge or 7 days post randomization, whichever comes first.
- Mortality rates at 30 days post-hospital discharge
- Mortality rates at 90 days post-hospital discharge
- Treatment-related SAEs up to 48 hours post-randomization

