15.3 Security, Privacy, and Confidentiality

VUMC employs several layers of data protection to ensure data security. The first part of security is physical protection of the hardware systems, access to which is limited to authorized personnel. By limiting access, ensuring only authorized personnel have access, and tracking all entry, we can ensure this risk is minimal. Additionally, REDCap has a built-in audit trail that tracks all user activity and changes made to the data entry fields with a date-time stamp.

16. Adverse Events

Adverse events (AE’s) may occur at any time after randomization. Pre-existing conditions (existing prior to randomization) will be documented in the subject’s medical record as part of prior medical history but will not count as an AE unless it worsens during the study. Adverse events (serious and non-serious) will be documented on an Adverse Event form. Non-serious adverse events will be recorded from randomization through hospital discharge or 7 days post-randomization (whichever is earlier). Serious adverse events will be recorded from randomization through the end of study (i.e., 90 day post-randomization follow-up).

Investigators will record characteristics of each adverse event on an Adverse Event form. Each adverse event will be judged by the Investigator as to its level of relatedness to the investigational devices and investigational procedure. In addition, the Investigator will identify the date of onset, severity and duration. Severity will be judged using the scale noted in Table 10. All adverse events will be monitored until they are adequately resolved or explained or until the subject reaches the end of the study.

Table 10. Definition of event severity for judgment by Investigator.

Term	Definition
Mild	Patient is aware of a sign or symptom, but that sign or symptom does not interfere with normal activity or symptom is both transient and resolved
Moderate	Symptoms interfere with the subject’s usual activity or symptoms require treatment
Severe	Symptom(s) cause either severe discomfort or have a significant impact of the subject’s usual activity and symptoms require treatment

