16.1 Serious Adverse Events

An adverse event is considered serious if it:

- Resulted in death
- Resulted in permanent impairment or damage
- Required inpatient hospitalization or prolongation of existing hospitalization
- Required medical or surgical intervention to prevent any of the above outcomes

As the last above bullet point references, an important medical event that may not result in death, be life-threatening, or require hospitalization may be considered a serious adverse event when, based upon appropriate medical judgment, the event may jeopardize the subject and may require medical or surgical intervention to prevent one of the outcomes listed in this definition. Examples of such medical events include (but are not limited to): allergic bronchospasm requiring intensive treatment in an emergency room or at home; blood dyscrasias or convulsions that do not result in inpatient hospitalization; or, the development of drug dependency or drug abuse. Serious adverse events should not be reported for hospitalization or prolonged hospitalization in the following scenarios: for a diagnostic or elective surgical procedure related to a pre-existing condition; to allow for an efficacy measure for the study; or, for a planned surgical procedure that was not the result of a condition worsening due to participation in the study.

An assessment should be made regarding the seriousness, severity and relationship to the investigational devices and investigational procedure. The following factors should be considered when evaluating causality of adverse events: 1) the temporal sequence from the study procedure; 2) patient's response after discontinuation or re-introduction; and, 3) severity of the event. The investigators, on the basis of their clinical judgment and guided by the following definitions, should determine the relationship of an adverse event to the administration of the investigational device, and/or study procedure(s) as: definitely related, i.e. following in a reasonable temporal sequence, known to be a complication, and having no other explanation; probably related, i.e. following in a reasonable temporal sequence and not reasonably explained by the patient's clinical state or other therapies; possibly related, i.e. could have been explained by other therapies or patient's clinical state; or not related.

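### Two SAE definitions and two relatedness ratings stand unreconciled, and late asymptomatic hemorrhage other than SAH falls outside the recording window of a 90-day primary safety outcome

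*Combined protocol and SAP*

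**What the plan says.** **Seriousness.** Section 5.9.3 states: "A serious adverse event is one that is fatal or life-threatening, is permanently or substantially disabling, requires or prolongs hospitalization". It then adds an open criterion, "any event that the treating clinician judges to be a significant hazard, contraindication, side effect, or precaution". Its footnote says: "Asymptomatic hemorrhage events are not considered serious adverse events". Section 16.1 begins "An adverse event is considered serious if it" and lists four conditions: death, permanent impairment or damage, new or prolonged hospitalization, and intervention needed to prevent any of these. It then exempts certain hospitalizations from SAE reporting.

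**Relatedness.** In section 5.9.3 the attending physician classifies each event's relation to the study treatment as "definitely related, probably related, possibly related, unlikely related, or not related". In sections 16 and 16.1 the Investigator judges relation to the investigational devices and procedure as definite, probable, possible or not related.

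**Recording.** Section 16 says: "Non-serious adverse events will be recorded from randomization through hospital discharge or 7 days post-randomization (whichever is earlier"; section 16.2 repeats the limit. SAEs are recorded until the 90-day visit, death or withdrawal of consent. Table 1, however, marks adverse event assessment at 30 days, 90 days and study closure.

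**Outcomes.** The seven primary safety outcomes in section 7.5.1 include "Treatment-related SAEs up to 48 hours post-randomization" and "Intracranial hemorrhage within 90 days of hospital discharge". Procedure-related SAEs are a secondary endpoint in sections 3.2 and 7.4.1.

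**The concern.** A count of treatment-related SAEs rests on two decisions per event: is it serious, and is it related? The protocol gives two answers to each and does not say which section prevails. The treating Investigator is not blinded (section 7.6), so any latitude is exercised with knowledge of the arm. The same counts go to the DSMB, which under section 7.5.2 monitors treatment-related SAEs and all SAEs.

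The 90-day hemorrhage outcome is not limited to symptomatic bleeds. The asymptomatic ones are classed as non-serious, and non-serious recording stops by the time this outcome's clock starts. Sites that follow the rules as written would return an incomplete count for a primary safety outcome.

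**Working it through.** The plan gives no figure to reproduce here. The check is a comparison of text, followed by a comparison of windows.

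**1. The two sets of rules side by side**

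| Item | Section 5.9.3 | Sections 16 and 16.1 |
|---|---|---|
| Life-threatening | Listed | Not in the bullets; mentioned only in the explanatory text |
| Open clinician judgement | Yes | No |
| Intervention to prevent a listed outcome | No | Yes |
| Hospitalization carve-outs | No | Yes |
| Asymptomatic hemorrhage | Never an SAE | Not addressed |
| Relatedness levels | 5 | 4 |
| Rater | Attending physician | Investigator |
| Object of the rating | Study treatment | Devices and procedure |

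Three consequences follow.

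- *Seriousness.* An asymptomatic hemorrhage that prolongs the hospital stay meets the hospitalization bullet of 16.1 but is excluded by the footnote to 5.9.3.
- *Levels.* An event rated unlikely under 5.9.3 has to become either possible or not related under 16.1. If related means possible or higher, only the move to possible changes the count.
- *Object.* Under 5.9.3 a medical-arm event can be related to its assigned treatment. Under section 16 a patient who had no device or procedure can hardly have a related event. Safety outcomes are compared as randomized (section 6.1.1), so the choice of section changes what the comparison between arms means.

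The only stated cut-off for related (definitely, probably or possibly) is in section 16.2. It governs the Medical Safety Monitor's safety reports, not the outcome in 7.5.1.

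**2. Non-serious recording against the hemorrhage outcome**

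Count days from randomization and let D be the day of discharge.

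- Non-serious recording ends at min(D, 7).
- The outcome window runs from D to D + 90.
- Since min(D, 7) ≤ D, the overlap is 0 of 90 days for every D. If D > 7, recording also stops D − 7 days before the window opens; for D = 14 that is 7 days.
- If the outcome is instead read as 90 days from randomization, the overlap is at most 7 days: 7/90 ≈ 8%.

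**3. SAE recording against the same outcome**

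Let V be the day of the 90-day visit. Section 4.4 allows ± 14 days, so V runs from 76 to 104. The part of the window after SAE recording ends is max(0, D + 90 − V). The documents give no length of stay, so D is assumed.

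| D (assumed) | V = 76 | V = 90 | V = 104 |
|---|---|---|---|
| 5 | 19 days | 5 days | 0 |
| 7 | 21 days | 7 days | 0 |
| 14 | 28 days | 14 days | 0 |

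Even a symptomatic hemorrhage can therefore fall after recording has closed. The 90-day mortality outcome in 7.5.1 is also timed from discharge and shares this tail, but none of the other problems.

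**4. Reach**

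The definitions, ratings and non-serious recording limit touch two of the seven outcomes in 7.5.1: treatment-related SAEs up to 48 hours, and intracranial hemorrhage within 90 days of discharge. The two 24-hour hemorrhage outcomes are supported by the required 24-hour scan and fall inside the recording window. The complications outcome closes at the same point as non-serious recording.

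**The case against.** The strongest reply is that the gap is narrower than it looks, and much of that reply stands.

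- *Recording.* A reader might infer that late asymptomatic hemorrhage has no recording route at all. The documents do not support that. Section 5.9.3 asks for a detailed form and narrative for asymptomatic SAH with no day-7 limit, and says adverse events are assessed at scheduled visits. Table 1 agrees. The text contradicts itself rather than being silent, and what remains exposed is asymptomatic hemorrhage other than SAH.
- *Detection.* Table 1 schedules no routine scan after 24 hours, and section 5.9.2.1 mentions imaging only to day 7. Late asymptomatic bleeds would be found incidentally, so few may be lost.
- *Safety reporting.* A reader might infer that a site rating of possible triggers expedited handling. Under section 16.2 every SAE is reported within 24 hours whatever its relatedness. The safety report depends on the Medical Safety Monitor's own view that the event is serious, unexpected and related.
- *Life-threatening events.* A reader might infer that these are lost under 16.1. Its explanatory text treats them as a marker of seriousness, and 16.2 sends serious or life-threatening events to the Monitor. Most would also meet another bullet. The open criterion and the carve-outs are the larger differences.
- *Unseen documents.* Events go onto one Adverse Event form, which may already impose one scale. Section 7.5.2 defers monitoring detail to an SAP and a Monitoring Plan. None of these is in the supplied text.

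None of this reconciles the two sections. A form that follows one of them would still contradict the other.

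**Conclusion.** The point holds in this form. Two SAE definitions and two relatedness ratings are in force with no rule of precedence and no cut-off for related in 7.5.1. One primary safety outcome and one secondary endpoint can therefore be counted differently depending on the section followed. Separately, asymptomatic hemorrhage other than SAH falls outside the recording window of a primary safety outcome, and the end of that window can outlast SAE recording.

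The size in events cannot be given. The documents state neither an expected SAE rate nor the share of events that would be rated unlikely, so a percentage would be invention. The hemorrhage shortfall is probably small, given the imaging schedule.

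It would also go too far to say that the primary safety outcomes as a group cannot be counted, since five of the seven do not depend on these definitions or on the non-serious recording limit. Nor is it settled that the conflict affects formal testing. Procedure-related SAEs stand fifth in the list in 7.4.1, ahead of revascularization, but that section applies sequential testing to clinical efficacy endpoints. If the list is tested as it stands, this count could decide whether testing goes on.

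The conclusion assumes that the Adverse Event form, SAP and Monitoring Plan do not already resolve these points.

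**What to change.** 1. Use one SAE definition in 5.9.3 and 16.1, preferably by cross-reference. State whether life-threatening events, clinician judgement, required intervention and the hospitalization carve-outs belong to it, and how the asymptomatic-hemorrhage footnote fits with the hospitalization criterion.
2. Use one relatedness scale with one named rater and one named object that works in both arms. State the cut-off for related in 7.5.1, for example possible, probable or definite, which would match 16.2. The number of levels matters less than having a single scale.
3. Record every detected intracranial hemorrhage, whatever its seriousness, to the end of the outcome window. Restate that window as randomization to the 90-day visit so that it matches follow-up. Alternatively, restrict the outcome to symptomatic hemorrhage; its window would still have to match SAE recording.
4. Reconcile the non-serious recording limit in 16 and 16.2 with the 30-day, 90-day and closure assessments in Table 1.

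The cost is protocol wording and changes to the Adverse Event form, with no added visits or scans. Routine late imaging is not proposed, so the hemorrhage outcome would remain a count of detected events and should be described as such.

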6.1 Analysis of Primary Endpoint

6.1.1 Definition of Analysis Samples

- Target Population
The target population for the POSITIVE trial is patients who are at least 18 who have a clinical diagnosis of Acute Ischemic Stroke who are ineligible for or refractory to treatment with IV-tPA and able to begin the thrombectomy procedure within a 6-12 hour time window of symptom onset or time last seen normal and as selected by physiologic imaging criteria.
- Intent to Treat Sample
As the primary analysis, all efficacy and safety outcome measures will be analyzed under the intent-to-treat (ITT) principle. Under this principle, the evaluable sample includes all subjects who are randomized. Each subject will be analyzed according to the treatment group to which they were assigned at randomization.
- Per Protocol Sample
In addition to the defined ITT analysis sample, a per-protocol sample is defined as a subset of the ITT sample. This sample will be used for secondary sensitivity analyses of the primary and secondary outcomes. The per-protocol sample will include all randomized subjects that do not have the following protocol violations or deviations:
 - a. Eligibility violation
 - b. Treatment crossover
 - c. Missing 90 day primary outcome (not including missing due to death prior to the 90 days)

7. General Statistical Considerations

The POSITIVE Trial is a multicenter, randomized, Phase III clinical trial investigating the safety and efficacy of endovascular mechanical thrombectomy administration in acute ischemic stroke patients ineligible for or refractory to treatment with IV-tPA presenting within a 6-12 hour time window as selected by physiologic imaging criteria compared to best MT. The primary hypothesis to be tested is that treatment with endovascular mechanical thrombectomy will improve outcomes at 90 days as compared to the best MT group. Each eligible subject will be randomized in a 1:1 ratio to either the endovascular mechanical thrombectomy or the best MT treatment group with a stratified randomization by NIHSS (<20 vs. ≥20) within each center to balance randomization. This variable was chosen because of the known association with outcome. Randomization will take place centrally through the web-based REDCap database system. The centrally controlled randomization will help ensure the treatment balance at any interim analysis as well as in the final analysis.

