However, these trials are focusing on patients within the 8-hour time period. Several recent reports have suggested that with image based selection patients may be effectively treated beyond these strict time boundaries with good outcomes. [26-29] A five year pilot study from our institution utilizing a perfusion imaging based paradigm to select AIS patients, irrespective of time, for IAT with mechanical thrombectomy indicates that we can treat patients safely (90 day mortality rate 26%, symptomatic bleed rate 7%) and effectively (90 day mRS 0-2, 38%) outside of the traditional time windows. In this series, our average time to treat from the last time the patient was seen normal was 11.3 hours. Furthermore, the patient outcomes and complications in those treated after 8 hours were no different than those treated before 8 hours.[30 31] We have further combined our data with those from 2 other centers and found that in 247 patients there were no differences in patient outcomes in those treated beyond 8 hours as opposed to those treated less than 8 hours when selected by physiologic imaging.[32]

Intra-arterial (IA) thrombolysis within 6 hours and mechanical thrombectomy within 8 hours have been shown to be feasible methods by which to achieve revascularization and there are data which suggest that revascularization improves patient outcomes.[7 12 33-36]

Until now, there has not been a single trial showing efficacy of intra-arterial thrombectomy (IAT) over medical therapy. The POSITIVE trial was originally designed and approved by the FDA to evaluate mechanical thrombectomy to treat acute ischemic stroke (AIS) related to a large blood vessel occlusion (LVO). Since the trial began, there have recently been data released from four trials that all show overwhelming positive outcomes of IAT over medical therapy of patients presenting within 6 hours of AIS onset.[37-41]

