Due to this recent data, the POSITIVE trial halted enrollment of patients presenting within 8 hours of AIS on 11/08/2014, until the published data was available from these multiple trials. The final data from these trials was finally fully available on 2/11/15. The POSITIVE steering and executive committees, in discussion with the study investigators, decided to permanently halt patients presenting within 6 hours of AIS and to change the late time group from 8-12 to 6-12. The reason to halt enrollment in the early time group was due to the overwhelming data across multiple trials. The MR CLEAN trial demonstrated an absolute difference of 13.5% in rate of functional independence in favor of IAT over medical therapy (32.6% vs 19.1%). MR CLEAN was notable in that it randomized 500 patients in the Netherlands to IV-tPA vs IV tPA and IAT presenting within 6 hours of stroke onset.[38] More robustly, the ESCAPE trial favored IAT over medical therapy by an odds ratio of 2.6 with a significant reduction in mortality (10.4% vs 19.0%). The ESCAPE trial was halted after enrolling 316 patients at 22 centers around the world presenting within 12 hours of stroke onset. The trial required advanced imaging to select patients with LVO and ability to rapidly transition from diagnosis to IAT within 30 minutes.[39] Similarly, the EXTEND IA trial based in Australia, was halted after 70 patients were enrolled due to positive results in the MR CLEAN trial. Interim analysis found a marked improvement in ability to achieve functional outcome with IAT (71%) over medical therapy (40%).[41] This overwhelming data has created an environment where equipoise has been lost in patients presenting within 6 hours of AIS onset.

The ESCAPE trial, while overwhelmingly positive and treating patients out to 12 hours, unfortunately did not show a significant difference in patients treated between 6-12 hours. There was a signal in the direction of intervention (odds ratio 1.7), but this was not significant.[39] It should be noted that only 49 of the 316 patients were in this 6-12 hour time frame. This perhaps highlights the obvious absence of Level 1 data available in treating patients presenting with AIS beyond 6 hours. The POSITIVE trial is notable in that it will continue to evaluate patients out to 12 hours, requiring documentation with advanced imaging of LVO and emphasize selecting patients with small or no infarctions present at time of triage.

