7.3 Missing Data and Imputation Methods

Under the ITT principle, all patients who are randomized are included in the analysis. Therefore, missing data, especially in the outcome measures, can be problematic. Every effort is to be made to keep all missing data, particularly the Day 90 outcomes, to a minimum. Despite the clinical sites' best efforts, some missing data may be inevitable mainly due to lost-to-follow-up (LTFU). The number and proportion of subjects eligible for and compliant with each follow-up examination will be presented. Subjects who withdraw from the study will be tabulated with reasons for withdrawal. Since the primary endpoint is defined using mRS, subjects deceased during study follow-up will be scored as mRS 6. Other subjects not completing the 90-day follow-up visit will be categorized for the primary endpoint using the mRS as of the last available follow-up visit or discharge (whichever is later). As a sensitivity analysis, we will also perform analysis after excluding subjects without 90-day follow-up evaluations. Additional details will be provided in the Statistical Analysis Plan (SAP).

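### The primary ITT set is everyone randomized, with no limit to the 6-12 h window, so section 6.1.1 needs a sentence on any patients randomized before 6 h under earlier versions

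*Combined protocol and SAP*

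**What the plan says.** **The analysis set.** Section 6.1.1 makes intention-to-treat primary and defines it in one line: "Under this principle, the evaluable sample includes all subjects who are randomized". Section 7.3 repeats it: "Under the ITT principle, all patients who are randomized are included in the analysis". Neither names a time window, a protocol version or a date. The primary model in section 7.2 adjusts for NIHSS, center and listed prognostic variables, and has no term for time window.

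**The history.** The Introduction, which is current text and not an amendment log, says enrolment was already under way: "Since the trial began, there have recently been data released from four trials". It goes on to say that "the POSITIVE trial halted enrollment of patients presenting within 8 hours of AIS on 11/08/2014", and that the committees "decided to permanently halt patients presenting within 6 hours of AIS and to change the late time group from 8-12 to 6-12".

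**The question now asked.** The objective (3.1 and 6), exclusion 1 and section 7 concern 6-12 h. The first bullet of 6.1.1 describes a target population "able to begin the thrombectomy procedure within a 6-12 hour time window of symptom onset or time last seen normal". The first two secondary endpoints in 3.2 and 7.4.1 are expressly limited to the 6-12 h cohort. The primary endpoint bullet and 7.2 carry no such limit.

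**The per-protocol set.** It removes eligibility violations, crossovers and missing day-90 outcomes, without saying which protocol version decides what an eligibility violation is.

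**The concern.** The primary question is about 6-12 h, but the set that answers it is everyone ever randomized. If patients under 6 h were randomized under earlier versions, following 6.1.1 to the letter puts them into the primary test. The per-protocol analysis would not clearly take them out, because a patient who was eligible when randomized is not plainly a violation.

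The direction of the effect is predictable. The protocol regards the evidence of benefit in early patients as so strong that "equipoise has been lost in patients presenting within 6 hours of AIS onset". For 6-12 h it cites only one earlier trial's subgroup: "There was a signal in the direction of intervention (odds ratio 1.7), but this was not significant". Early patients would therefore move the pooled odds ratio and p-value toward benefit. At stake is the headline result, which could be positive while the same test in 6-12 h patients is not. If the text stays silent, the choice of set could also be made after results by arm are known.

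**Working it through.** **1. The plan's own figure.** Section 7.1 gives 180 patients for at least 80% power at an odds ratio (OR) of 2.1 under proportional odds, and 200 after 10% loss. With 1:1 allocation and two-sided 5% (stated for the secondaries, assumed for the primary), Whitehead's formula is

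N = 12(1.96 + 0.84)² / [(ln OR)² × f], where f = 1 − Σp̄³ and p̄ is the mean of the two arms' category proportions.

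The plan gives no control distribution. I assume 5/9/11/15/18/42% for mRS 0, 1, 2, 3, 4 and 5-6, which puts 25% at mRS 0-2. Then f = 0.948, ln 2.1 = 0.742, and N = 12 × 7.85 / (0.550 × 0.948) ≈ 181. Across five other assumed distributions N is 177 to 183. 180/0.9 = 200. The sample size reproduces and is not in question.

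**2. What mixing does, approximately.** Let a share s of the analysed patients be early. The pooled log-OR is roughly (1 − s) ln(OR at 6-12 h) + s ln(early OR). With 36 of 180 early, s = 0.20. With a 6-12 h OR of 1.0 and an early OR of 2.1, the pooled log-OR is 0.20 × 0.742 = 0.148, a pooled OR of 1.16. At that OR f ≈ 0.923, so the expected z is 0.148 × √(180 × 0.923/12) = 0.55. The two-sided rejection rate is Φ(0.55 − 1.96) + Φ(−0.55 − 1.96) ≈ 8.6%.

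**3. Simulation.** Assumptions: the control distribution above, 180 analysed, early OR 2.1, 6-12 h OR 1.0. The test is an unadjusted tie-corrected Wilcoxon test, which is the score test of the proportional odds model.

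| Early patients among 180 | Share | Primary rejects, two-sided | Primary favours thrombectomy, same ordinal test at 6-12 h fails |
|---|---|---|---|
| 0 | 0% | 4.9% | 0% |
| 10 | 5.6% | 5.2% | 1.3% |
| 18 | 10% | 5.8% | 2.3% |
| 36 | 20% | 8.4% | 5.6% |
| 54 | 30% | 13.0% | 10.5% |

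The last column uses the same test in both sets, so it isolates the effect of mixing. Set against the 6-12 h mRS 0-2 test instead, the figures are 2.3, 3.2, 6.2 and 11.0% for 10, 18, 36 and 54 early patients. About 1.4% of that occurs with no early patients, because an ordinal and a dichotomised test can disagree.

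**4. The safeguard.** Section 7.4.1 tests a 6-12 h secondary straight after a significant primary. With 10 to 54 early patients, the chance that both reject when there is no 6-12 h effect is about 2% if that secondary is mRS 0-2 (order in 7.4.1), and 2.5 to 3.7% if it is the mRS distribution (order in 3.2). Both stay below 5%.

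**5. A less extreme 6-12 h effect.** If the 6-12 h OR is the quoted 1.7, the pooled OR is 1.72, 1.74, 1.77 and 1.81 at 5, 10, 20 and 30% early patients. If the 6-12 h OR is 1.0, it is 1.04, 1.08, 1.16 and 1.25.

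**The case against.** The strongest reply is that the context already supplies the limit. The 6-12 h target population stands directly above the intention-to-treat bullet, and the objective, exclusion 1 and section 7 agree with it. That makes a 6-12 h set the likely intent. It does not settle the matter, because the target population says whom the trial is for and the next bullet, which defines the set, is broader. If everyone analysed were 6-12 h, the cohort limit on the secondaries would be redundant.

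A second reply is that every figure above rests on an assumed early count and, for the table, on no effect at all at 6-12 h. This stands. Section 7.3 also defers detail to a statistical analysis plan. If a separate one already limits the set, only a cross-reference is needed.

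A reader might infer more than the documents support:

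- *That early patients were randomized and will be pooled.* The Introduction shows the early group was open to enrolment. It gives no count and does not say that anyone under 6 h was randomized.
- *That a 6-12 h claim would have an inflated error rate.* The hierarchy prevents this for any claim made through the 6-12 h secondaries.
- *That 200 is too few.* Power at 6-12 h falls only if early patients count toward the 200. With 20 early and 10% loss, 162 remain and power is about 76%; with 60 early, 126 remain and it is about 65%. Section 7.1 attaches the 200 to the revised trial, so the natural reading is 6-12 h patients only.

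**Conclusion.** The point holds as a gap in the definition of the primary analysis set. Sections 6.1.1 and 7.3 admit any earlier patient under 6 h, and nothing in 7.2 or the per-protocol definition clearly removes or separates them. The size cannot be known from the documents. The effect is negligible for about 10 early patients, or if the 6-12 h effect is close to the early one. It becomes material with about a fifth or more early patients together with little effect at 6-12 h. The harm is to the primary odds ratio and p-value, not to formal 6-12 h claims. It is worth fixing because the change is small and should not be left until results by arm are known.

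**What to change.** Before any outcome comparison by arm is seen, state in 6.1.1, and refer to it in 7.2 and 7.3, that the primary intention-to-treat set is:

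- (a) all patients randomized under the 6-12 h criteria, analysed as assigned and kept even if randomized outside the window in error; plus
- (b) earlier-version patients whose recorded time from onset or last seen normal to randomization was 6-12 h. This takes in the old 8-12 h group and any 6-8 h patients from the old early group.

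Time to randomization is fixed before assignment in both arms, so the rule respects intention-to-treat. Report earlier-version patients under 6 h separately. As a sensitivity analysis, pool all randomized patients with a window-by-treatment term. State that an eligibility violation is judged by the version in force at randomization, and confirm in 7.1 that the 200 counts only the primary set.

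**Cost.** Wording in four sections, with no new data in principle. Any early patients leave the headline analysis. The rule also assumes that onset times were recorded for earlier-version patients, which the documents do not state; the current exclusion of patients under 6 h cannot show it, because it did not apply to them. If no patient under 6 h was randomized, one sentence saying so replaces all of this.
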